### **8.3.3. Concomitant Medications**

Concomitant medications will be coded using the World Health Organization (WHO) Drug Dictionary (current version) and summarized to the therapeutic drug class, Anatomical Therapeutic Chemical (ATC) 4 classification, and preferred name.

### **8.3.4. Clinical Laboratory Data**

All hematology and chemistry laboratory assessments were performed by local laboratories.

The following protocol-specified clinical laboratory findings will be summarized using descriptive statistics.

1. Hematology:
  - a. Hemoglobin
  - b. Neutrophils (absolute and %)
  - c. Platelets
  - d. Reticulocyte count (percent and absolute reticulocyte)
  - e. White blood cells (WBCs)
2. Chemistry and Liver Function Tests:
  - a. Alkaline phosphatase
  - b. Alanine aminotransferase (ALT)
  - c. Aspartate aminotransferase (AST)
  - d. Indirect bilirubin
  - e. Total bilirubin
  - f. Lactate dehydrogenase (LDH)
  - g. Serum Erythropoietin

Change from baseline and the percent change from baseline will be summarized for the above laboratory results. Analyte units will be converted to International System of Units (SI) units.

Subject listings of laboratory data will include a separate listing for clinically significant laboratory results.

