Among the earliest manifestations of sickle-related organ damage is loss of splenic function in the first two years of life which places children at high risk of sepsis, particularly from encapsulated organisms such as *Streptococcus pneumoniae* and *Haemophilus influenzae*. Furthermore, renal concentrating ability is also impaired and signals the beginning of the decline in renal function that may lead to chronic renal failure and end-stage renal disease. Pain is also an important component of the disease and in young children, presents as dactylitis or hand-foot syndrome and can be the first sign of SCD. The most devastating complication of pediatric SCD is the development of central nervous system (CNS) events. This may present as overt stroke or silent strokes which are subclinical cerebral infarctions detected on brain magnetic resonance imaging (MRI). Almost 50% of the SCD population is pediatric (Farber, 1985) and approximately 11% of SCD patients have clinically apparent strokes before the age of 20 years. The risk of stroke is highest during the first decade, and it is most significant between ages 2 and 5, when it reaches 1.02% per year. In addition to overt strokes, another 17% to 22% of children suffer silent strokes which can produce significant neuropsychological deficits (Ohene-Frempong, 1998; Verduzco, 2009). The pathogenesis of stroke in children with SCD is complex and not fully resolved but in most cases involves occlusion or stenosis of the large intracranial arteries. Histopathology varies, but in general the pattern is one of smooth muscle proliferation with overlying endothelial damage and fibrosis (Rothman, 1986; Koshy, 1990). Smaller arterioles and capillaries show distention, thrombosis and vessel wall necrosis (Tuohy, 1997). Damaged, aberrant red cells adhere abnormally to the vascular endothelium and thereby trigger endothelial cell activation. Endothelial cell activation cascades into further disturbances, including a hypercoagulable state and abnormal vasomotor tone. The greater risk of stroke in young children with SCD may be explained by the higher cerebral blood velocity observed in this population (Powars, 2000).

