4.2. Exclusion Criteria

Any participant who meets one or more of the following criteria will be excluded from participation:

1. Any one of the following requiring medical attention within 14 days of signing the informed consent form (ICF):
 - Vaso-occlusive crisis (VOC)
 - Acute chest syndrome (ACS)
 - Splenic sequestration crisis
 - Dactylitis
2. Requires chronic transfusion therapy.
3. History of stroke or meeting criteria for primary stroke prophylaxis (history of two TCD measurements \geq 200 cm/sec by nonimaging TCD or \geq 185 cm/sec by TCDi).
 - For the potential modification, addition of approximately 20 participants enrolled in Part C, TCD \geq 170 cm/sec by nonimaging TCD or \geq 155 cm/sec by TCDi
4. Transfusion within 30 days prior to signing the ICF.
5. Renal dysfunction requiring chronic dialysis or creatinine \geq 1.5 mg/dL.
6. Hepatic dysfunction characterized by alanine aminotransferase (ALT) $> 4 \times$ upper limit of normal (ULN) for age.
7. Clinically relevant cardiac abnormality, in the opinion of the Investigator, such as:
 - Hemodynamically significant heart disease, eg, congenital heart defect, uncompensated heart failure, or any unstable cardiac condition.
 - An arrhythmic heart condition requiring medical therapy.
8. QTcF > 450 msec, congenital long QT syndrome, second or third degree heart block at rest (with the exception of asymptomatic Mobitz type I second degree heart block).
9. Received an investigational drug within 30 days or 5 half-lives, whichever is longer, of signing the ICF.
10. Heavy smoker (defined as smoking more than 10 cigarettes/day or its nicotine equivalent including e-cigarettes).

11. Unlikely to comply with the study procedures.
12. Other medical, psychological or addictive condition that, in the opinion of an Investigator, would confound or interfere with evaluation of safety and/or PK of the investigational drug, prevent compliance with the study protocol, or preclude informed consent.
13. Participants who do not have a TCD window (Part B and Part C only) (ie, participants who are unable to have a TCD due to skull ossification).
14. For Part C only, prior participation in Part B.
15. Active symptomatic COVID-19 infection.

In addition, for Part D only:

16. Body weight < 5 kg for 1 month prior to the screening visit and at the screening visit.
17. Any condition affecting drug absorption, such as major surgery involving the stomach or small intestine (prior cholecystectomy is acceptable).

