
 • Hematocrit • Hemoglobin • MCV • Platelet count • RBC count • RBC distribution width • Reticulocyte count (absolute and percent) • WBC count with differential (basophils, eosinophils, neutrophils, monocytes, lymphocytes) • Hb electrophoresis^a 	
 • Albumin • Alkaline phosphatase • ALT • AST • Bicarbonate • Bilirubin (total, direct, and indirect) • BUN • Calcium^b • Chloride • Creatinine • GGT^b • Glucose • LDH • Magnesium^b • Phosphorus^b • Potassium • Serum erythropoietin • Sodium • Total protein

Abbreviations: ALT, alanine aminotransferase; AST, aspartate aminotransferase; BUN, blood urea nitrogen; GGT, gamma-glutamyl transferase; Hb, hemoglobin; LDH, lactate dehydrogenase; MCV, mean corpuscular volume; RBC, red blood cell; WBC, white blood cell.

^a Hb electrophoresis will be performed at Screening only.

^b These tests will be performed at Screening and more frequently if clinically indicated.

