10.3.2. Safety Data

All safety assessments will be conducted on the Safety population.

A TEAE is defined as an AE that emerges on or after initiation of study drug (having been absent pretreatment), or an AE that existed pretreatment and worsened on treatment (relative to the pretreatment state). The number and percentage of participants reporting TEAEs will be tabulated by MedDRA® (current version) system organ class and preferred term, severity and relationship to study medication. Serious TEAEs and TEAEs resulting in discontinuation of study drug will be summarized separately.

Concomitant medications will be mapped using the WHODRUG dictionary (current version). The number and percentage of participants taking each concomitant medication will be tabulated.

Analysis of laboratory results will be based on those reported by the local laboratory at each site. Continuous laboratory measurements will be descriptively summarized at each visit for observed values and changes from baseline.

Vital signs and ECG parameters (based on average of triplicate measurements) will be summarized at each visit for observed values and changes from baseline. In addition, QT and QTc intervals will be summarized categorically as number and percentage of participants with abnormal values or increases.

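### Part D SAP 8.3.4 limits the chemistry summary to seven analytes, none renal or electrolyte, although protocol 10.3.2 provides for by-visit summaries of continuous laboratory measurements

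*SAP*

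**What the plan says.** Protocol 10.3.2 sets the general rule: "Continuous laboratory measurements will be descriptively summarized at each visit for observed values and changes from baseline". It is not restricted by analyte or study part.

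Protocol Table 5 (section 5.4.1) gives the Part D tests under two columns, hematology and serum chemistry. The chemistry column includes creatinine ("Chloride • Creatinine • GGT^b • Glucose • LDH") and potassium and sodium ("Potassium • Serum erythropoietin • Sodium • Total protein"), as well as BUN and bicarbonate. Four chemistry items carry the footnote "These tests will be performed at Screening and more frequently if clinically indicated". Appendix 7 schedules serum chemistry at every Part D visit. Unlike Appendix 5 for Part C, it has no urinalysis.

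Part D SAP 8.3.4 begins "The following protocol-specified clinical laboratory findings will be summarized using descriptive statistics". It then names five hematology items and seven chemistry and liver items: alkaline phosphatase, ALT, AST, indirect bilirubin, total bilirubin, LDH and erythropoietin. It adds: "Change from baseline and the percent change from baseline will be summarized for the above laboratory results". Other laboratory values go to subject listings, with a separate listing of clinically significant results. Part D SAP section 2 states that its methods supersede the protocol's where applicable.

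**The concern.** Safety and tolerability is the primary objective of Part D, and clinical laboratory tests are a named safety endpoint (Part D SAP 3.1 and 4.4). The protocol treats the kidney as relevant in this population. Section 1.1 says of early organ damage that "renal concentrating ability is also impaired and signals the beginning of the decline in renal function", and section 4.2 excludes participants with "Renal dysfunction requiring chronic dialysis or creatinine" at or above 1.5 mg/dL. The endpoint nevertheless loses its whole renal and electrolyte component at the summary stage. With no urine tests, serum values are the only laboratory data on renal function that Part D schedules.

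A modest shift across the group is the kind of finding that case-by-case review tends to miss. Each value is judged by an investigator against a local laboratory's normal range, with approximately 25 sites planned for the study. A group shift shows only when values are pooled by visit, and the SAP does not pool these.

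**Working it through.** The plan gives no figure on this point to reproduce. The check compares what is collected with what is summarised.

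**Step 1. Chemistry collected in Part D.** Protocol Table 5 has 21 analytes when total, direct and indirect bilirubin are counted separately.

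**Step 2. Sort them by the treatment they get in Part D SAP 8.3.4.**

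| Status | Analytes | Count |
|---|---|---|
| Summarised | alkaline phosphatase, ALT, AST, indirect bilirubin, total bilirubin, LDH, erythropoietin | 7 |
| Scheduled after Screening, not summarised | albumin, bicarbonate, direct bilirubin, BUN, chloride, creatinine, glucose, potassium, sodium, total protein | 10 |
| Screening only unless clinically indicated, not summarised | calcium, GGT, magnesium, phosphorus | 4 |

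7 + 10 + 4 = 21, so 14 of 21 get no summary, and 10 of those 14 are measured during treatment.

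**Step 3. Renal and electrolyte items.** Six are among the 10 on-treatment omissions: creatinine, BUN, sodium, potassium, chloride and bicarbonate. Three more (calcium, magnesium, phosphorus) are among the Screening-only items. That makes 6 + 3 = 9 collected, with 0 of 9 in the Part D list.

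**Step 4. Compare the other parts.** Parts A/B SAP 8.3.4 and Part C SAP 7.3.4 each include one of these nine, potassium. Neither includes creatinine or BUN. So the creatinine and BUN gap is common to all three SAPs. The loss of potassium and the absence of any urine data are specific to Part D.

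**Step 5. Is the list closed, and is the narrowing declared?** The list is introduced as the findings that follow, with no wording that makes it illustrative. The SAP calls it protocol-specified, but the protocol specifies all of Table 5 and defines no subset. The Parts A/B SAP has a section on changes in the planned analyses (section 10) and a statement that further tables may be added (section 11). The Part D SAP has neither.

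**Step 6. Other routes to a table.** Protocol 5.4.1 and 9.3.4 send an abnormality to the adverse event form only if it is judged clinically significant and, under 9.3.4, needs active management. Those cases reach the TEAE tables. A shift below that level does not.

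**The case against.** Several points on the other side are sound.

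- **Protocol 10.3 leaves analysis details to the SAP, which supersedes the protocol.** A reader might infer a breach of the protocol or an open conflict over which text governs. The documents do not support that: the SAP list governs. What remains is a narrowing with no stated reason.
- **Other outputs exist.** A reader might infer that a renal change would be invisible everywhere. It would not. All values can be read in listings for about 30 children, and clinically significant abnormalities, including those that prompt extra follow-up or investigation, reach the adverse event tables. What is lost is the pooled view of a sub-clinical shift.
- **The named drug risks lie elsewhere.** The protocol names gastrointestinal events, rash, hypersensitivity and possible tissue hypoxia, and the laboratory triggers for dose modification are hepatic. The renal passage in section 1.1 describes the disease. With a single arm, a drift could not be attributed to the drug. This limits interpretation, but it applies equally to the analytes that are summarised.
- **A summary table would not be sensitive.** A reader might infer that it would reveal a mean creatinine rise of 10 to 15%. The documents give no creatinine variability. Assume an SD of the log ratio to baseline of 0.2 to 0.3. The upper 95% margin, exp(t × SD/√n) − 1, is then 7.8 to 11.9% at n = 30 and 15.4 to 23.9% at n = 10, the minimum size of the youngest group. A 10 to 15% rise is not distinguishable from zero in that group and is only partly so overall. The case for adding the rows is complete reporting of a safety endpoint.
- **The 1.5 mg/dL limit.** A reader might treat it as the on-study alarm level. It is an entry criterion. During the study, detection rests on investigator judgement and CTCAE grading.

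**Conclusion.** The point holds as an unexplained narrowing of a safety summary. In Part D, 7 of 21 chemistry analytes are summarised. Ten that are scheduled after Screening are not, and these include all six renal and electrolyte items measured throughout treatment. A sub-clinical group shift in those six, in children aged 6 months to under 4 years, would appear in no laboratory summary table.

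This conclusion rests on reading the enumerated list as closed, which its wording supports, and on counting the three bilirubins separately. It assumes nothing about variability or about any renal effect of the drug, and the documents give no evidence of such an effect.

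**What to change.** In Part D SAP 8.3.4, add creatinine, BUN, potassium, sodium, chloride and bicarbonate to the chemistry list, with observed value, change and percent change by visit. In Part C SAP 7.3.4, add creatinine and BUN.

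With these additions Part D summarises 7 + 6 = 13 of the 17 chemistry analytes scheduled after Screening. For the remaining four (albumin, direct bilirubin, glucose, total protein), one sentence saying that their omission is deliberate would remove the mismatch with protocol 10.3.2.

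The cost is a few more rows in tables already planned. The samples are already drawn, so no visit or procedure changes.

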### **8.3.5. Vital Signs and Physical Exam**

Vital signs, including systolic and diastolic blood pressure and heart rate, will be summarized using continuous descriptive statistics at each visit. Change from baseline will also be summarized for each post-baseline visit.

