	
The PK parameters to be determined will include C_{max}, AUC, $t_{1/2}$, and percent Hb occupancy.
 
Plasma and whole blood concentrations will be determined using validated liquid chromatography/ mass spectrometry (LC/MS) methods.

Safety Assessments	
Participant safety and tolerability will be monitored during the study using standard measures, including physical examinations, vital signs (including blood pressure, pulse rate, body temperature, respiratory rate), 12-lead electrocardiograms (ECGs, collected in triplicate) (Parts A, B, and C only), clinical laboratory tests, concomitant medication usage, and adverse event (AE) monitoring.
 
For Parts B and C, TCD measurements are being obtained to determine a preliminary treatment effect. However, abnormal values can indicate a safety concern and will be followed up as appropriate for standard clinical care.

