1.6. Risk Assessment

Based on the mechanism of action of voxelotor and findings in the nonclinical safety toxicology studies, voxelotor could cause tissue hypoxia. In GLP toxicology studies, rats dosed for 28 days with ≥ 250 mg/kg/day demonstrated increased erythropoietin and red cell mass (hematocrit [Hct], RBC, or Hb) with extramedullary hematopoiesis and bone marrow hypercellularity. These findings are consistent with expected physiologic compensation to hypoxia, were well tolerated in the rat, were not considered adverse, and were reversible.

In prior clinical experience with other agents, no adverse reactions related to tissue hypoxia were reported at the highest tested doses of tucarsesol administered in either healthy participants (maximum 40% Hb-modification) or participants with SCD (maximum 24% Hb -modification), or BW12C infusions in either healthy participants (maximum 40% Hb -modification) or participants with SCD (23% Hb modification) (Arya, 1996 ; Keidan, 1986; Nicholls, 1989; Rolan, 1995). Appropriate acute and chronic compensatory physiologic responses to tissue hypoxia were observed, including an increase in heart rate during moderate exercise and a slight increase in reticulocyte counts at high doses (Nicholls, 1989; (Rolan, 1995; Rolan, 1993). Importantly, healthy participants were well-compensated both at rest and at near maximal exercise with little change in resting heart rate (Nicholls, 1989). Potential tissue hypoxia can be monitored by hematology laboratory studies, erythropoietin levels, and cardiovascular parameters.

Gastrointestinal effects (primarily emesis, and soft or liquid feces) were observed in all species and were dose-limiting in dogs and monkeys. Gastrointestinal erosions, ulcers, or epithelial hyperplasia were observed at high doses in rats.

The most common AEs with an incidence of at least 20% were headache and diarrhea (Vichinsky, 2019). The majority of these TEAEs were Grade 1 or 2 in severity. The percentages of participants who had a Grade 3 event, a serious adverse event (SAE), and/or treatment discontinuation due to an AE did not differ substantially among the 3 treatment arms (1500 mg voxelotor, 900 mg voxelotor, or placebo).

In addition, the decline in erythropoietin levels suggest an improvement in oxygen delivery either by increase in hemoglobin or improvement in microvascular blood flow, or both (Vichinsky, 2019; Howard, 2019).

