5.3. Clinical Assessments

Screening assessment must be conducted within 28 days prior to initiation of dosing for Part A, and within 35 days prior to initiation of dosing for Parts B, C, and D. Laboratory assessments, vital signs and physical examinations conducted on Day 1 predose may be conducted on Day -1. Refer to [Appendix 1](#), [Appendix 3](#), [Appendix 5](#), and [Appendix 7](#) for additional details.

Clinical assessments, including weight, vital signs, ECGs, AEs, and concomitant medications will be conducted at specified time points during the study (refer to [Appendix 1](#), [Appendix 3](#), [Appendix 5](#), and [Appendix 7](#)). Vital signs data to be collected include supine systolic and diastolic blood pressure, pulse rate, respiration rate and temperature (in °C). 12-lead ECGs will be collected in triplicate. Any other medical condition present at baseline should be followed during the study, and a change from the baseline status (intensity or frequency) should be reported as an AE if deemed clinically significant by the Investigator (refer to Section 9).

Height and weight will be recorded as outlined in [Appendix 1](#), [Appendix 3](#), [Appendix 5](#), and [Appendix 7](#). There is no weight restriction for Parts A, B, or C of the study. Height (in centimeters) and weight (in kilograms) should be measured with the participant's shoes off. Head circumference will be recorded in Part D as outlined in [Appendix 7](#).

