**7.3.5. Vital Signs and Physical Exam**

Vital signs, including systolic and diastolic blood pressure, heart rate, respiratory rate, temperature, and weight will be summarized using continuous descriptive statistics at each visit and time point. Change from baseline will also be summarized for each post-baseline visit.

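### Part D summarises heart rate and blood pressure without an age reference, so late-visit changes mix a year's growth with any drug effect; adding one would be a cheap improvement

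*SAP*

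**What the plan says.** Protocol section 1.6 names tissue hypoxia as a possible consequence of the drug's mechanism and says how it can be followed: "Potential tissue hypoxia can be monitored by hematology laboratory studies, erythropoietin levels, and cardiovascular parameters". Vital signs are a listed Part D safety endpoint (Protocol 3.9.4.4; Part D SAP 4.4).

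The Part D SAP, section 8.3.5, plans: "Vital signs, including systolic and diastolic blood pressure and heart rate, will be summarized using continuous descriptive statistics at each visit". It continues: "Change from baseline will also be summarized for each post-baseline visit". Nothing in that section refers the values to age, and no categorical summary is planned. Section 8 of the same SAP presents results in two age groups (6 months to under 2 years, 2 to under 4 years) and overall.

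On which signs are covered:

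- Protocol 5.3, on collection: "Vital signs data to be collected include supine systolic and diastolic blood pressure, pulse rate, respiration rate and temperature".
- Part C SAP 7.3.5: "Vital signs, including systolic and diastolic blood pressure, heart rate, respiratory rate, temperature, and weight will be summarized".
- Part D SAP 8.3.5 names blood pressure and heart rate only.
- Protocol 10.3.2, for the study as a whole: "Vital signs and ECG parameters (based on average of triplicate measurements) will be summarized at each visit for observed values and changes from baseline".

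Part D vital signs are scheduled at Screening, Day 1, Weeks 2, 4, 8, 12, 16, 20, 24, 36 and 48, and follow-up (Protocol Appendix 7). ECGs are scheduled at Screening only, with more if clinically indicated (Protocol 5.4.5; Part D SAP 8.3.6).

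**The concern.** Resting heart rate and blood pressure depend on age in infants and toddlers. I take that as background; the documents give no reference values. A child who enters at 9 months and finishes at about 20 months would be expected to change on no treatment at all. With one arm and no age reference, the mean raw change at a late visit estimates growth plus drug effect, and the planned tables do not separate the two.

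The two age groups do not solve this. They stop infants being pooled with three-year-olds, but every child still ages by the full treatment period within its group.

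The direction matters most for heart rate. If it normally falls with age, a drug-related rise of similar size would leave the late-visit mean near zero, and a smaller rise would look like a fall. Safety is the primary objective of Part D, so the late-visit tables should be readable on this point.

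**Working it through.** The plan states no figure to reproduce. Part D has no alpha, power, effect size or SD, and no expected heart-rate change.

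**Inputs from the documents.** Treatment lasts 48 weeks (Protocol 8.1). About 30 children are planned, at least 10 of them under 2 years (Protocol 3.1.4). The visits are those in Appendix 7.

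**Assumed inputs.** Age-related fall in resting heart rate of 5, 10 or 15 beats/min per year; drug-related rise of 10 beats/min; SD of change 15 beats/min (range 10 to 20).

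**Step 1: drift by visit.** Drift = annual fall × weeks/52. At Week 48 the time factor is 48/52 = 0.92.

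| Visit | 5 per year | 10 per year | 15 per year |
|---|---|---|---|
| Week 2 | 0.2 | 0.4 | 0.6 |
| Week 4 | 0.4 | 0.8 | 1.2 |
| Week 12 | 1.2 | 2.3 | 3.5 |
| Week 24 | 2.3 | 4.6 | 6.9 |
| Week 36 | 3.5 | 6.9 | 10.4 |
| Week 48 | 4.6 | 9.2 | 13.8 |

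This counts from Day 1. The SAP baseline averages all pre-dose assessments, and Screening may be 35 days earlier. With one Screening and one Day 1 value, the effective baseline is up to 2.5 weeks earlier, which adds at most 15 × 2.5/52 = 0.7 beats/min.

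**Step 2: what a constant 10 beats/min rise would look like.** Raw mean change = 10 − drift.

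- Week 4: +9.6, +9.2, +8.8.
- Week 12: +8.8, +7.7, +6.5.
- Week 48: +5.4, +0.8, −3.8.

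The rise is nearly intact early and can vanish or reverse by Week 48.

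**Step 3: drift against precision.** The 95% half-width is t(0.975, n−1) × SD/√n. At SD 15 it is 5.6 beats/min for n = 30 and 10.7 for n = 10. Over SD 10 to 20 it is 3.7 to 7.5 and 7.2 to 14.3. The Week 48 drift is therefore comparable with the sampling error in many of these cases.

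**Step 4: Week 48 only.** The chance that the 95% interval lies wholly above zero, from the noncentral t with SD 15 and a true rise of 10, is:

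| n | Age-referenced | Raw, fall 5 | Raw, fall 10 | Raw, fall 15 |
|---|---|---|---|---|
| 30 | 0.94 | 0.48 | 0.05 | <0.01 |
| 10 | 0.47 | 0.17 | 0.035 | <0.01 |

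The age-referenced column assumes a reference that fits exactly and leaves the SD unchanged. No such test is planned. The figures only show how much the late-visit display depends on growth, and they do not describe the by-visit series.

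**The case against.** The strongest reply is the visit schedule. Vital signs are summarised at every visit, and the Protocol (5.7.5) treats Day 28 as steady state. By Step 1 a sustained early rise would be visible at Weeks 2 to 12 and would then appear to shrink. The follow-up visit about four weeks after the last dose, for children who do not enter the extension, adds an off-drug comparison with drift of only 0.4 to 1.2 beats/min. This stands. A reader might infer that growth would hide the hypoxia signal altogether, and the documents do not support that. What remains is a rise that starts late, or whether an early rise has persisted.

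Second, hypoxia monitoring does not rest on vital signs. Part D SAP 8.3.4 summarises hemoglobin, reticulocytes and erythropoietin with absolute and percent change. This also stands, with limits. A hemoglobin rise is the intended effect, yet Protocol 1.6 also describes increased red cell mass as compensation for hypoxia in rats. Hydroxyurea titration is permitted in Part D. Erythropoietin is scheduled on treatment only at Weeks 24 and 48. Protocol 1.6 also says of an earlier agent that "healthy participants were well-compensated both at rest and at near maximal exercise with little change in resting heart rate"; that tempers the expected resting signal, but it comes from healthy participants.

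Third, a reader might infer that respiratory rate has been dropped, or that a stated hypoxia monitor has been lost. Neither follows. The Part D list opens with the word including, Protocol 10.3.2 covers vital signs generally, and the hypoxia sentence in 1.6 does not name respiratory rate. It is unnamed in Part D and named in Part C, which is a matter of consistency.

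Finally, the slope is assumed. No masking figure is offered for blood pressure, since the documents give neither the size nor the direction of its age trend. Age-standardising would not remove the effects of rising hemoglobin or of hydroxyurea changes.

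**Conclusion.** The point holds as a low-severity reporting improvement. In an uncontrolled 48-week study of very young children, raw change at Weeks 24 to 48 cannot be read as a drug effect on heart rate or blood pressure, and the two age groups do not repair this. Under the assumed fall of 5 to 15 beats/min per year, the heart-rate drift grows from about 0.4 to 1.2 beats/min at Week 4 to 2.3 to 6.9 at Week 24 and 4.6 to 13.8 at Week 48. A late-onset or persisting rise could be understated by about that much at the late visits.

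The size rests wholly on the assumed slope. That the two sources are mixed rests only on the design and on these signs changing with age. No sample size, power figure or primary endpoint is affected.

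**What to change.** In Part D SAP 8.3.5:

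1. Keep the raw summaries by visit.
2. Add heart rate and systolic and diastolic blood pressure as z-scores or centiles for age at the visit, with change from baseline.
3. Add the number of children outside pre-specified age-specific limits at any post-baseline visit, above and below separately. These limits are for tabulation only and carry no rule for managing a child.
4. Name respiratory rate in the list, as Part C SAP 7.3.5 does.
5. State that these results will be read beside erythropoietin and hemoglobin.

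The cost is a few lines of SAP text, an age reference chosen before the data are reviewed, and programming. No new data or visits are needed. The drawback is that a reference drawn from other children may not describe anemic children exactly. That could shift the level of the z-scores and the counts outside limits; change from baseline is less exposed, provided the reference's age slope is about right. Keeping the raw tables lets the reader see both.
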